4.2 Recruitment Methods

PD subjects will be recruited from the University of Michigan (U-M) Movement Disorder Center (MDC), which follows a population of about 2,000 clinically well-defined patients with PD. An additional source of subjects will be the VAAAHS Movement Disorders Clinic (directed by [name]). This clinic follows over 240 Veterans with idiopathic PD and this clinic serves as a tertiary referral center for more advanced PD subjects coming from the tri-state area (MI, north-western Ohio and eastern Indiana) resulting in a larger than average referral of new patients. PD and PSP subjects from previous studies who have indicated interest (initials in informed consent form) in new studies at our laboratory will also be contacted. In case of unforeseen need, additional recruitment of subjects is possible via local Parkinson support groups and the Michigan Parkinson Foundation. Data Direct (<https://datadirect.med.umich.edu/>) will be used to recruit patients at Michigan Medicine to be study participants. A flyer will also be used to recruit subjects.

Screening script: Screening script will be used if subjects do not wish to discuss the study further with a staff member or consent to the study in the clinic. In the past, subjects have expressed interest and discussed the study with staff members. However, they don't want to consent at that time and wish to go home and think about it. Study team members will follow-up with these subjects and use the screening script before subject comes in, to prevent wasted travel and time of the subject. Also, subjects recruited via other methods will be screened using the screening script.

Timetable: The main study, to be conducted over a 4-year period, will include a gross total of n=64 patients with PD (allowing for a net recruitment of n=56 given possible attrition (10-12%)), due to imaging claustrophobia, unexpected brain imaging findings etc. 16 subjects will be enrolled annually. Up to 20 PSP participants will be enrolled over the 4-year period to participate. The study will continue after the main study portion is complete to allow for the collection of limited follow-up data at 3 years (± 1 year) from last study visit and then again at 2 years (± 1 year) post the previous follow-up visit.

Compensation: Subjects will not be charged for their participation in this study. Subjects will receive \$100 for the completed PET scan and \$100 for the MRI scan. Payment for completion of the Screening/Baseline Visit will be \$200. Subjects that participate in the additional optional follow-ups for the exploratory aim will receive \$25 for each follow-up visit. Subjects will be

financially compensated for lost time and effort. We estimate that about 2/3 of PD/PSP patients will also need one night of overnight lodging to accommodate for “off state” requirements. Cost for overnight lodging and meals are estimated at \$280 per night (3 nights per person). Subjects will receive a voucher for valet parking at the University Hospital. Parking at Domino's Farms is free. Subjects will be paid after their last study visit or, in case they decide to withdraw from the study, they will be paid for the parts that they have completed.

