We have novel preliminary data showing that non-acute vestibulopathy may be another important factor contributing to PIGD motor features, in particular FoG in PD and PSP. Unlike sporadic intermittent vestibular disorders with a more acute onset, chronic bilateral vestibular dysfunction of older age (recently defined by the Bárány Society as presbyvestibulopathy, PVP) is also common in PD (5-7). Our preliminary data suggest that PVP may be a critical determinant of FoG in PD (scientific premise). Furthermore, we found that absence of PVP was associated with a very low frequency of FoG suggesting a specific effect of PVP on FoG in PD. However, these preliminary observations need to be confirmed in a larger study using more dedicated assessment methods (knowledge gap). Closing this gap is important because of the potentially high clinical translational impact if our preliminary findings can be verified. The overarching goal of this study is to test the hypothesis that the presence of PVP is an important risk factor for FoG in subjects with PD and PSP while accounting for nigrostriatal dopaminergic denervation.

Contents

Protocol Title:	1
1.0 Study Personnel	4
2.0 Introduction	4
3.0 Objectives	10
4.0 Study Procedures.....	10
4.1 Study Design	10
4.2 Recruitment Methods.....	15
4.3 Informed Consent Procedures.....	117
4.4 Inclusion/Exclusion Criteria.....	117100
4.5 Study Evaluations.....	118
4.6 Data Analysis	20
4.7 Withdrawal of Subjects	23
5.0 Reporting.....	23
6.0 Privacy and Confidentiality	23
7.0 Communication Plan	24
8.0 References	25

Protocol Title:

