The significance of this project is that it addresses an unmet need in clinical practice, i.e. there is currently no effective treatment for FoG in advancing PD or in PSP. Our preliminary data suggest that PVP may be a critical determinant of FoG. Assessment of postural

vestibular sensory deficits in PD patients with FoG and patients with PSP may provide a better understanding of pathomechanisms of FoG that may inform therapeutic management.

IMPACT & FUTURE DIRECTIONS

New knowledge from this project may provide important clues about the pathophysiology of motor freezing behaviors and associated risk of falls in PD. Such clues may inform novel therapeutic interventions for this unmet clinical need. Falls and postural instability are a major clinical dilemma in patients with PD. These issues get progressively worse and more difficult to treat as the disease progresses. New therapies to reduce FoG and imbalance in patients with PD and PSP may reduce fall risk and drastically improve functional abilities and quality of life of these patients.

Preliminary Studies

We present novel preliminary findings of a significant association between presence of FoG and PVP clinical status and evidence of an independent relationship between abnormal VOR function, PIGD motor features and postural control that cannot be explained by other PD specific features such as bradykinesia or rigidity.

i) **Association between clinical presence of FoG and PVP in persons with PD.** We investigated the relationship between the clinical presence of FoG and PVP in persons with PD. Methods: 92 patients with PD (M70/F22; mean age 67.6 ± 7.4 years, mean motor disease duration 6.0 ± 4.6 years, mean Hoehn and Yahr stage 2.4 ± 0.6) completed detailed clinical assessment. FoG status was defined by direct observation of motor freezing behavior by an experienced neurologist while performing the UPDRS motor examination. Clinical screening for PVP was performed using the modified Romberg sensory conflict test (1). A time to fall < 20 seconds while standing on foam surface with eyes closed was used for the presence of PVP as previously reported (1), and validated in a prior study of patients with vestibular disorders (34). **Our findings showed a substantially higher frequency of FoG in PD persons with PVP (33%) compared to PD persons without PVP (3.3%; Likelihood ratio $\chi^2=15.6$; $P<0.0001$), see table 1. Furthermore, PVP was present in the majority (84.6%) of PD persons with FoG.**

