[¹¹C]DTBZ dopaminergic brain PET imaging was available in 29 patients. Logistic regression analysis of this subset showed that **the PVP effect remained highly significant (Likelihood ratio $\chi^2=10.3$; $P=0.0013$) independent from the degree of nigrostriatal dopaminergic losses.** Similar independent significant effects for the PVP effect (Likelihood ratio $\chi^2=7.1$; $P=0.0070$) was seen when adjusting the model for effects of age or the severity of parkinsonian motor impairments. These preliminary data suggest that PVP may be an important factor contributing to FoG independent of the degree of disease-specific confounders.

Table 1. Contingency table of FoG vs. clinical PVP status in PD
(Likelihood ratio $\chi^2=15.6$; $P<0.0001$)

	No PVP	PVP	Total
No FoG	57	22	79
FoG	2*	11**	13
Total	59	33	92

*FoG was present in 3.3% in PD persons without PVP

[figure not shown]
**PVP was present in 84.6% of PD freezers

ii) VOR and PIGD features in PD and PSP. VOR was assessed in 29 PD patients (9 female, 67.8 ± 6.9 years of age, 5.9 ± 3.2 years of motor disease duration) using the active head rotation (AHR) protocol of the VORTEQ™ module of the VisualEyes™ VNG system. The two main outcome parameters were gain (ratio of slow component eye velocity and head velocity) and phase (offset in eye movement time relative to the head movement). All subjects underwent the MDS-UPDRS clinical examination for assessing PD severity. Separate sub-scores were calculated for PIGD, bradykinesia, tremor, and rigidity features. We dichotomized phase into “normal” and “abnormal”, with $-5^\circ \leq$ normal phase $\leq 5^\circ$. PIGD sub-score was dichotomized into “low” and “high” based on a median split (score of 6). Chi-square analysis was performed to test for difference in proportion normal/abnormal phase between the two PIGD groups (see **Table 2**). Near significant analysis ($\chi^2=3.1$, $p=0.077$) showed that there were disproportionately more PD subjects with abnormal VOR phase in the group with high PIGD sub-scores (see also **Figure 1**).

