4.4 Inclusion/Exclusion Criteria

Eligibility criteria:

1. Diagnosis:
 - PD based on the United Kingdom Parkinson's Disease Society Brain Bank Diagnostic Research Criteria (n=64, gross; M/F, age 45 years or older), with duration of disease > 5 years and/or Hoehn & Yahr stages 1.5-4 and able to ambulate independently.
 - PSP following the Movement Disorder Society Revised 2017 diagnostic criteria for PSP across a spectrum of severity of disease (modified Hoehn & Yahr stages 1-4) (n=up to 20). PSP diagnosis will be verified by a clinician using the PSP-RS and other clinical information collected from the medical history. Participants meeting the diagnostic criteria for probable PSP, as determined by a clinician, will be eligible. (Investigator discretion).
2. Dementia will be excluded by cognitive screening assessment and assessment of instrumental activities of daily living (PDCFRS).

Exclusion criteria:

1. History of Meniere disease or recent onset of acute vestibular dysfunction, such as otolith disorders (BPPV etc).
2. Other disorders which may resemble PD, vascular dementia, normal pressure hydrocephalus, multiple system atrophy (MSA), corticobasal ganglionic degeneration, or toxic causes of parkinsonism. Prototypical cases have distinctive clinical profiles, like early and severe dysautonomia (MSA) or appendicular apraxia, which may differentiate them from idiopathic PD and PSP. The use of the UKPDSBRC clinical diagnostic criteria for PD will mitigate the inclusion of subjects with atypical parkinsonism.
3. Evidence of a stroke or mass lesion on structural brain imaging (MRI).
4. Participants in whom MRI is contraindicated including, but not limited to, those with a pacemaker, presence of metallic fragments near the eyes or spinal cord, or cochlear implant.
5. Severe claustrophobia precluding MR or PET imaging.
6. Subjects limited by participation in research procedures involving ionizing radiation.
7. Pregnancy (test within 48 hours of each PET session) or breastfeeding.
8. Subjects with active and unstable mood or anxiety disorders
9. Subjects with active ear infections or perforated eardrums

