We propose to test the overall hypothesis that the prevalence of FoG is higher in subjects with PD and PSP who also have evidence of PVP compared to those without vestibulopathy independent of nigrostriatal dopaminergic losses. We will begin by calculating summary statistics (mean, median, SD, range, etc.) as well as plots of all data. This will allow us to examine the distribution of the data to ensure that assumptions of statistical models will be respected. All analysis will be performed using the R statistical software package. We predict that the prevalence of freezers will be higher in the PVP group compared to the non-PVP group. We will recruit a PD population enriched for the presence of FoG by requiring at least 5 years of motor disease duration and exclude participants with early-stage Hoehn & Yahr disease. Given the prevalence of FoG in about 50% of patients in this group we expect to recruit about even groups of freezers and non-freezers. Our preliminary data showed that PVP was present in $p_1= 84.6\%$ of PD freezers and $p_2=27.8\%$ in non-freezers. Given our net recruitment target of $n=56$ (half of whom will be freezers) PVP will be present in just over half of the total study population (56.2%). We plan to build a predictive model, such as logistic or probit, that links the binary FoG response to PVP (a binary variable) and the DAT PET scan (linear variable). Power is set at 0.8 with a significance level of 0.05 and the rejection region is one sided: $p_1 > p_2$. Sample size for PD is estimated based on preliminary data that yield estimates for p_1 and p_2 (as outlined above), and using the R-module statmod and calling the function power.fisher.test which simulates data sets – in our case we set its parameter nsim=1000 data sets -- to generate required sample sizes for given power and including the dopamine PET scan preliminary findings. We will recruit up to 20 PSP participants to ensure an adequate sample size is used and to account for possible attrition.

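### Recruitment may bring members of the 92-patient preliminary cohort into the study meant to confirm that cohort's finding, and the plan neither records nor separates them

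*Combined protocol and SAP*

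**What the plan says.** The opening summary gives the purpose: "these preliminary observations need to be confirmed in a larger study using more dedicated assessment methods".

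The preliminary observations are the team's own. Section 2.0 (Preliminary Studies) describes "92 patients with PD (M70/F22; mean age 67.6 ± 7.4 years" and further characteristics. PVP was found in 11 of 13 freezers and 22 of 79 non-freezers (Table 1). Section 4.6 introduces its planning rates with "Our preliminary data showed that PVP was present in" and gives 84.6% of freezers against 27.8% of non-freezers.

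Section 4.2 lists the recruitment sources: a university clinic following about 2,000 PD patients, a VA clinic following over 240, and then "PD and PSP subjects from previous studies who have indicated interest" in new studies at the laboratory. Support groups, a records search tool and a flyer are also named. The preliminary cohort is not excepted.

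Section 4.4 admits PD patients "with duration of disease > 5 years and/or Hoehn & Yahr stages 1.5-4 and able to ambulate independently". Neither the inclusion nor the exclusion list mentions earlier participation. Section 4.6 has no flag, covariate, subgroup or sensitivity analysis for it.

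**The concern.** An association noticed in one sample needs testing in other patients. If some of the same patients return, they tend to bring back the PVP split that prompted the hypothesis. The new estimate is then pulled toward the preliminary one, and a significant result is only partly independent evidence.

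The documents leave room for this. The cohort's mean motor disease duration (6.0 years) and mean Hoehn and Yahr stage (2.4) largely fit the PD criteria. PVP is classified by the same rule in both studies; for the preliminary cohort, "A time to fall < 20 seconds while standing on foam surface with eyes closed was used for the presence of PVP". The net target of 56 implies about 28 freezers, and the preliminary cohort contained 13.

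Without a record of who was in that cohort, nobody can show afterwards that the overlap was negligible.

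**Working it through.** **The plan's own figures first.** Table 1 gives 11/13 = 84.6% and 22/79 = 27.8%, with mean (84.6 + 27.8)/2 = 56.2%, as section 4.6 states. The likelihood-ratio chi-square recomputes to 15.5 (stated 15.6). Exact power of the one-sided Fisher test at 0.7 against 0.3 with 24 per group is 0.836, in line with the stated 0.82 or greater. The power calculation is not in question.

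**Inputs from the documents.** 28 freezers and 28 non-freezers (half of the net 56 each); one-sided 0.05; returning freezers drawn from 11 with and 2 without PVP; returning non-freezers drawn from 22 with and 57 without.

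**Assumptions, not in the documents.**
- k freezers and k non-freezers return (written k+k).
- Each keeps the earlier PVP status with probability r. Otherwise the status is redrawn at the new-participant rate for that group. Full persistence is r = 1, half is r = 0.5.
- FoG status does not change.

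**Method.** The PVP count in each group is a hypergeometric draw of k from the preliminary cohort, modified by r, plus a binomial count for the other 28 - k. The rejection rate is the summed probability of all tables with one-sided Fisher p at or below 0.05. This is exact enumeration.

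**Result 1: no association in new participants (PVP 50% in both groups).**

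| Returning | Half persistence | Full persistence |
|---|---|---|
| none | 2.4% | 2.4% |
| 1+1 | 2.8% | 3.3% |
| 2+2 | 3.3% | 4.5% |
| 4+4 | 4.5% | 7.8% |
| 8+8 | 8.1% | 20% |
| 13+13 | 15% | 50% |

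The starting value is 2.4% because the exact test is conservative at this size. The choice of 50% matters little: with a common PVP rate of 35.9% or 56.2%, the rate is 2.6-2.9% with no overlap, and at 3+3 it is 4.2-4.7% (half) or 6.4-7.1% (full).

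**Result 2: modest true association (60%/40%).** The odds ratio is (0.6/0.4)/(0.4/0.6) = 2.25. With 8+8 and full persistence the expected PVP rates are:
- freezers: (20 × 0.6 + 8 × 0.846)/28 = 0.670
- non-freezers: (20 × 0.4 + 8 × 0.278)/28 = 0.365

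The odds ratio of these two rates is about 3.5; with half persistence it is about 2.8. The chance of significance moves from 31% to 47% (half) or 63% (full).

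**Result 3: the plan's own rates (70%/30%).** With 8+8 the chance of significance moves from 86% to 91% (half) or 94% (full).

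**Room to set patients aside.** 56 - 48 = 8. If these are 4 freezers and 4 non-freezers, 24 per group remain, with power 0.836. At 22 per group power would be 0.778.

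**The case against.** Overlap is possible but not documented. Nothing says that the 92 patients gave permission for recontact or belong to the pool in section 4.2, and the other sources are far larger. If recruits came in proportion from the two clinics and all 92 were among their patients, about 56 × 92/2,240 = 2.3 of the 56 would be returning. That is itself an assumption, and targeted recontact could raise it. Section 4.6 also states another route to freezers: enrichment by disease duration and stage. This stands, and it is why the size can only be given as a range that includes zero.

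The outcome is also measured differently. The preliminary cohort was classified by observation during the UPDRS motor examination. Section 4.1 now uses the NFOG-Q and/or a provocation protocol, reclassifies questionnaire-negative patients who freeze, and has videos scored by an unaffiliated neurologist. An earlier non-freezer can become a freezer. This also stands. It weakens carry-over without removing it, because the Romberg rule is unchanged and both conditions plausibly persist.

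Finally, the planned model adjusts for DAT PET, whereas the Fisher test is the planning test. Preliminary PET covered only 29 patients, with a different tracer, so the adjusted result would rest largely on new imaging. That is fair, but PVP and FoG status enter that model too.

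A reader might infer that the study re-counts its preliminary data, or that the 13 known freezers will fill the freezer group and make a false positive a coin toss. The documents support neither. No stored data are reused, and the 50% figure needs all 13 freezers to be contactable, eligible, willing and unchanged, together with 13 non-freezers.

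**Conclusion.** The point holds as a gap in the plan: the confirming study can enrol patients who generated the hypothesis, and nothing would reveal how many did. It is not evidence that overlap will occur, and it does not invalidate the design.

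The harm depends on an unstated number. Under the assumptions above, up to about 2+2 returning patients leave the rejection rate below the nominal 5%. At 4+4 it is 4.5-7.8% and at 8+8 it is 8.1-20%. The effect matters most if the true association is weaker than planned; at 70%/30% the conclusion would seldom change.

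Re-measurement does not settle the matter. Re-testing the same people shows that their status persists, not that the association holds in other patients. The issue concerns PD participants only, since the preliminary cohort had no PSP patients. The optional return visits of this study's own participants are a separate matter.

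**What to change.** Add to sections 4.4 to 4.6:
- Record at enrolment whether each PD participant was in the 92-patient preliminary cohort.
- Report the overlap count, by FoG group.
- Prespecify that the PVP-FoG estimate is also reported without those participants, and that the result is described as independent confirmation only to the extent that this second estimate supports it.

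Earlier participants need not be barred. The cost is one data field and one more run of the same model, or one sentence if the overlap is zero. The downside is a somewhat smaller set for the second estimate: it stays at or above the plan's minimum of 48 for up to 8 overlapping patients, if they split evenly between freezers and non-freezers. Beyond that its power falls short of the planned 0.80 (0.778 at 22 per group), and the report should say so.

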4.3 Informed Consent Procedures

Prior to any research procedures, IRB-approved written informed consent will be obtained from each subject followed by initial study eligibility screening. A study team member will obtain consent in a private location at the Functional Neuroimaging, Cognitive, and Mobility Lab, or Ann Arbor VA Movement disorders clinic. Remote electronic consent may be obtained using SignNow to reduce physical interaction between study staff and subjects.

4.4 Inclusion/Exclusion Criteria

Eligibility criteria:

1. Diagnosis:
 - PD based on the United Kingdom Parkinson's Disease Society Brain Bank Diagnostic Research Criteria (n=64, gross; M/F, age 45 years or older), with duration of disease > 5 years and/or Hoehn & Yahr stages 1.5-4 and able to ambulate independently.
 - PSP following the Movement Disorder Society Revised 2017 diagnostic criteria for PSP across a spectrum of severity of disease (modified Hoehn & Yahr stages 1-4) (n=up to 20). PSP diagnosis will be verified by a clinician using the PSP-RS and other clinical information collected from the medical history. Participants meeting the diagnostic criteria for probable PSP, as determined by a clinician, will be eligible. (Investigator discretion).
2. Dementia will be excluded by cognitive screening assessment and assessment of instrumental activities of daily living (PDCFRS).

Exclusion criteria:

1. History of Meniere disease or recent onset of acute vestibular dysfunction, such as otolith disorders (BPPV etc).
2. Other disorders which may resemble PD, vascular dementia, normal pressure hydrocephalus, multiple system atrophy (MSA), corticobasal ganglionic degeneration, or toxic causes of parkinsonism. Prototypical cases have distinctive clinical profiles, like early and severe dysautonomia (MSA) or appendicular apraxia, which may differentiate them from idiopathic PD and PSP. The use of the UKPDSBRC clinical diagnostic criteria for PD will mitigate the inclusion of subjects with atypical parkinsonism.
3. Evidence of a stroke or mass lesion on structural brain imaging (MRI).
4. Participants in whom MRI is contraindicated including, but not limited to, those with a pacemaker, presence of metallic fragments near the eyes or spinal cord, or cochlear implant.
5. Severe claustrophobia precluding MR or PET imaging.
6. Subjects limited by participation in research procedures involving ionizing radiation.
7. Pregnancy (test within 48 hours of each PET session) or breastfeeding.
8. Subjects with active and unstable mood or anxiety disorders
9. Subjects with active ear infections or perforated eardrums

